Caffeinated chewing gum improves sympathetic nerve activity and simulates wrestling performance: a double-blind crossover trial

Document Date: Dec 25, 2024

IRB approved date: March 3, 2024

Project summary

The purpose of this study was to investigated whether caffeine intake is effective in improving the performance of wrestlers in a simulated competition. The study was designed to involve 16 healthy adult male athletes who had been trained in professional wrestling and were divided into caffeine trial (CAF trial) and placebo trial (PL trial) in a randomized crossover double-blind study design. After three days of dietary control, participants arrived at the laboratory in the afternoon of the day of the trial to collect saliva samples in a quiet state and were fitted with a heart rate monitor. Participants chewed either caffeine-containing gum at 3 mg/kg body weight (CAF trial) or placebo-containing gum without caffeine (PL trial) for 10 minutes and then spit it out. Participants then underwent a 15-minute dynamic warm-up. At the end of the warm-up, participants performed 2 rounds of 3-minute wrestling-specific simulated matches, and the number of falls in the simulated matches was recorded. After the simulation match, saliva samples were collected from the participants again. The saliva samples were analyzed for caffeine alpha-amylase concentration. Differences between the two trials were analyzed using a paired sample t-test and significance was set at $\alpha < 0.05$.

Introduction

At the Olympic Games and the World Athletics Championships, wrestling is one of the most popular event. In addition to specialized skills, the key to winning a wrestling match is muscle strength and anaerobic power (1, 2). In a previous study, 92 male wrestlers were divided into elite and non-elite groups according to their performance, and it was found that absolute muscular strength and anaerobic power were the key factors that differentiated elite wrestlers from non-elite wrestlers(2). From these studies, it appears that improving strength as well as anaerobic power of a wrestler is an important factor in winning a competition.

Many studies have suggested that caffeine (1,3,7-trimethylxanthine) supplementation prior to exercise is effective in improving maximal muscle strength and anaerobic capacity, with approximately small to moderate improvements (3). It has been established that the mechanisms in question consist of antagonised adenosine receptors.

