It has been demonstrated that chewing caffeinated gum can enhance the rate of caffeine absorption, leading to a more expeditious attainment of the maximum blood concentration of caffeine(10). The absorption of caffeine from chewing caffeine gum is a process that occurs through the mucous membrane of the oral cavity. The rate of absorption is such that the highest concentrations of caffeine in the blood can be reached within approximately fifteen minutes after chewing (11). With regard to the effects of caffeine on exercise performance, studies based on systematic reviews and meta-analyses have found that the ingestion of caffeine chewing gum at a dose greater than 3 mg/kg of body weight prior to exercise can effectively improve maximal muscular strength and anaerobic power (12). In the case of weight classes being required for events such as wrestling, the caffeinated chewing gum has been demonstrated to reduce water intake and may decrease the risk of being overweight. This may serve as an additional effective method of supplementing caffeine intake. The purpose of this study was to investigate the effect of caffeinated chewing gum on sympathetic nerve activity on wrestling simulation match.

Methods

Study design

In this study, a double-blind crossover experimental design was used, in which participants were randomised to either the caffeinated chewing gum trial (CAF) or the placebo chewing gum trial (PL). After a seven-day washout period, the participants were switched to another trial of experiments (Figure 1). All tests were conducted after a regular 6-day training period with a day off to ensure that participants were in a similar physiological state prior to the experiment. Prior to the experiment, participants were asked to perform at least 2 simulated matches to familiarise with the simulated matches before the main experiment. The primary outcome measure was the number of falls in the simulated match, while the secondary outcome was α -amylase concentration in saliva, as an indicators of sympathetic nerve activity. The study commenced on 11 June 2024 and concluded on 23 December 2024.

Participants

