All the experiments were conducted at 3pm. Upon arrival at the laboratory, the participants were required to undergo saliva collection. Three milliliters of saliva were spat into a saliva tube for later analysis. After the participants putted on heart rate monitor, participants were instructed to chew either caffeine-containing gum (3 mg/kg body weight) or a caffeine-free placebo gum for a period of 10 minutes. Thereafter, the gum was to be expectorated. Following this, the participants underwent a dynamic warm-up for a period of 15 minutes. It has been established that the highest blood concentration of caffeine is achieved 15 minutes after the chewing of the gum and subsequent expulsion(11). After warming up, participants are permitted to engage in any form of self-stimulation they deem appropriate, including yelling, punching the dummy, and other similar actions. The present action has been meticulously designed to enhance sympathetic nerve activity. This finding serves to corroborate the hypothesis that caffeine supplementation exerts a stimulant effect on sympathetic nerve activity.

After warming up, the grip strength of the participant's hands was measured with a grip strength meter (Smedley's Hand Grip Dynamometer TTM, Tokyo, Japan). Subsequently, participants engaged in a 3-minute, 2-round simulated wrestling match. This simulation has been shown to have good reliability and validity(14). In each 3-minute round of the simulation, one dummy fall was performed in the first 30 seconds, with an interval of 10 seconds each time. The participants then try to complete the maximum number of falls in 20 seconds. After the fall, the participants were given a 10-second break for a total of 1 minute. The same pattern was followed in the 2nd and 3rd minutes. During the 3rd minute, the duration of continuous wrestling was extended to 30 seconds. After a 30-second break, the participant repeated the same simulation and record the total number of falls. After the simulation competition, saliva was collected again and caffeine concentration and α -amylase concentration were measured.

Caffeine and placebo gum

The caffeinated chewing gum employed in the present study (Military Energy Gum, Arctic Mint flavour; Stay Alert, Chicago, USA) has been utilised in previous studies(7, 10). It is estimated that a single piece of gum contains approximately 5 grams and 100 milligrams of caffeine. The placebo gum was a commercially available blue mint gum

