(Lotte Gum Mint., Ltd., Tokyo, Japan). In order to administer a dose of 3 mg/kg of caffeine per unit of body weight, it was necessary to crush, grind, blend, reshape and flavor all chewing gums with 0.3 g of peppermint-flavored powder. The process was designed to ensure that the new chewing gums were comparable to the original in terms of appearance, color, flavor, weight and size. Previous studies have demonstrated that this method renders it impossible for the participant to distinguish the type of gum (7, 15).

Saliva sample collection and analysis

Saliva samples were stored in a refrigerator at -80 degrees immediately after collection. For analysis, samples were thawed and centrifuged at 4000 rpm for 5 min. 500 μ L of saliva samples were transferred to glass tubes for mass spectrometry analysis and Enzyme-linked immunosorbent assay (ELISA) analysis respectively. The analysis of saliva α -amylase concentration was conducted utilising an enzyme-linked immunosorbent assay (ELISA) with commercially available reagents (Neogen Corporation, Kentucky, USA; Salimetrics LLC, State College, PA, USA).

Statistical analysis

All data are presented as means \pm standard deviations. The Shapiro–Wilk test was utilised to evaluate the normality of the data. The grip strength and number of fall on each rounds between the two trials were analyzed using paired t-tests. The saliva caffeine and α -amylase concentration and RPE were analyzed using two-way ANOVA with repeated measures. If the interaction effect (trial \times time) were significant, the Bonferroni method was used to perform post hoc comparisons. Effect sizes were calculated using Cohen's d to quantify the magnitude of observed effects and defined as trivial (<0.20), small (0.20 – 0.40), moderate (0.40 – 0.80), and large (>0.8), respectively. The power value of each data was conducted using G*Power 3.1.9.6 software (13).

Reference

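### The primary outcome is falls in the match, but the only stated falls test is round by round, with no rule for combining the two rounds, so the primary test is not fixed

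*Protocol*

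**What the plan says.** Five places in the protocol bear on the primary test.

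- **Study design** defines the outcome at match level: "The primary outcome measure was the number of falls in the simulated match".
- **Methods, Protocol subsection** describes the match: "participants engaged in a 3-minute, 2-round simulated wrestling match". After the break between rounds, "the participant repeated the same simulation and record the total number of falls". The natural reading is a total over both rounds, although the sentence does not say so.
- **Statistical analysis** is the only section that assigns tests to individual variables. For falls it says: "The grip strength and number of fall on each rounds between the two trials were analyzed using paired t-tests". It adds that "the Bonferroni method was used to perform post hoc comparisons", but only after a significant trial-by-time interaction. That ties the step to the repeated-measures ANOVAs of saliva caffeine, α-amylase and RPE.
- **Project summary** gives a general statement, "Differences between the two trials were analyzed using a paired sample t-test", with a significance level of 0.05. It does not say whether the total or each round is compared, or whether the test is one- or two-sided.
- **Dates**: "The study commenced on 11 June 2024 and concluded on 23 December 2024" (Study design), and "Document Date: Dec 25, 2024" (title block).

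**The concern.** A primary outcome needs one test, or a stated rule for several. Here the outcome is one quantity per match, while the analysis produces two p-values for falls, neither of them for that quantity.

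Followed as written, the analysis gives no single answer. If one round is significant and the other is not, nothing in the text says whether the primary outcome was met. The error rate of the primary claim then depends on a rule that a reader has to guess:

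- If either round may carry the claim, the false-positive rate exceeds 5%.
- If both rounds are needed, it falls well below 5%.
- If the total is tested once, it is 5%.

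The Bonferroni step does not help, because it does not cover falls.

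**Working it through.** **Reference point: the protocol's own figure.** The sample size section takes 56.8 ± 2.0 s against 52.9 ± 1.8 s, an effect size of 2, alpha 0.05, and arrives at 6 participants. The pooled-SD effect size is 3.9 / √((2.0² + 1.8²)/2) = 3.9 / 1.903 = 2.05, which agrees with 2. For one paired t-test with standardised difference 2.0 at two-sided 0.05, the noncentral t distribution gives n = 6 at 95% power (achieved 97.1%). The 95% is an assumption, because the protocol states no power. So the stated 6 is reproduced for **one** comparison, whereas the analysis section provides two for falls.

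**Inputs for the error rates.**

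- From the protocol: n = 16 analysed, 2 rounds, significance level 0.05.
- Assumed: two-sided tests; normally distributed round differences (CAF minus PL); correlation ρ between the two round differences of 0, 0.5, 0.8 or 0.9. The protocol gives no value for ρ. The 0.80 in its sample size section enters a different calculation and does not supply it.

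**Method.** Each round gives t = mean difference / (SD of differences / √16) on 15 degrees of freedom. The critical value is 2.131 at 0.05 and 2.490 at 0.025. Under no effect in either round, 400,000 trials were simulated per value of ρ.

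| Rule for a positive primary result | ρ = 0 | ρ = 0.5 | ρ = 0.8 | ρ = 0.9 |
|---|---|---|---|---|
| Either round, either direction, 0.05 each | 9.7% | 9.2% | 7.9% | 7.1% |
| Increase in either round (single test: 2.5%) | 4.9% | 4.6% | 4.0% | 3.6% |
| Both rounds, 0.05 each | 0.3% | 0.8% | 2.1% | 2.8% |
| One test on the total, 0.05 | 5.0% | 5.0% | 5.0% | 5.0% |
| Either round, 0.025 each | 4.9% | 4.7% | 4.1% | 3.7% |

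Analytic check at ρ = 0: 1 − 0.95² = 9.75% and 1 − 0.975² = 4.94%, which agree with the first two rows. Repeat simulations agree to about 0.1 percentage point.

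**How often would the rounds disagree?** Take an illustrative true standardised difference of 0.6 in both rounds (assumed). Exactly one round is then significant in 33% of trials at ρ = 0.5 and in 21% at ρ = 0.8. At ρ = 0.5 the chance of a positive result is 45% if both rounds are required and 78% if either suffices.

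**The case against.** **The protocol can be read consistently.** The Project summary and the Methods together can suggest a paired t-test on total falls. Alternatively, if each three-minute round counts as a simulation in its own right, a per-round test matches the outcome. Neither reading settles the matter. The summary sentence is generic: it sits alongside saliva measurements that the analysis section assigns to ANOVA, and it never names the total. Treating each round as a match conflicts with the Methods, which describe one match of two rounds, and it would still leave two unadjusted primary tests.

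**Such details belong in a statistical analysis plan.** That would answer mere silence. Here the protocol does state an analysis of falls, and that analysis does not fit its own primary outcome.

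**The inflation is conditional.** This stands. The 7.1% to 9.7% applies only if either round may count, and the correlation is unknown. A false claim of an increase stays below 5% under every rule shown. The figures show how much depends on the unstated rule; they do not show that an error occurred.

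**The total is not the only valid choice, and the dates prove nothing about when the analysis was chosen.** Both stand. Naming one round, or requiring both, would also fix the test. Ethics approval in March 2024 leaves room for an earlier text that fixed it. New wording now cannot restore prespecification, so disclosure of timing matters as much as the choice itself.

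**Conclusion.** The concern holds. The protocol states one match-level primary outcome and an analysis that yields two round-level tests with no way to combine them. Depending on the rule a reader supplies, the two-sided false-positive rate of the primary claim lies anywhere from 0.3% (both rounds, ρ = 0) to 9.7% (either round, ρ = 0), against 5.0% for one test on the total. These figures rest on n = 16, two-sided testing, normal differences and assumed correlations from 0 to 0.9.

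That the primary test is unfixed follows from the text alone and needs none of these assumptions. It should be fixed: the possible inflation is modest and conditional, but it bears on the trial's main claim.

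**What to change.** In the Statistical analysis section, state one primary analysis: a two-sided paired test at 0.05 on total falls over rounds 1 and 2, CAF minus PL, with its 95% confidence interval. Label the per-round tests secondary. If the per-round tests are to remain primary, test each at 0.025 or use Holm, and state what counts as success.

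Also state whether the choice was made before the data were seen. If it was not, label it post hoc.

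The cost is one or two sentences plus that disclosure, with no new data. Per-round claims become secondary. The effect on power runs both ways. For an illustrative standardised difference of 0.6 (assumed), a single round tested alone at 0.05 has 61% power in a round where the effect is present.

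- **Effect in one round only:** the total has standardised difference 0.6/√(2 + 2ρ), which is 0.35 at ρ = 0.5 and 0.32 at ρ = 0.8, and power of about 25% and 22%.
- **Same effect in both rounds:** the total has 1.2/√(2 + 2ρ), which is 0.69 and 0.63, and power of about 74% and 66%.
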